**Non-Hematologic Toxicity ≥ Grade 3:**

Hold drug until recovery to grade 1 or baseline then resume with a reduction in dose by 1 capsule each of Dec and THU. If recurrent toxicity occurs, interrupt drug administration and after recovery from the toxicity, resume therapy with a decrease in frequency of administration to 1X/week. The overall goal is to sustain regular administration at a lower dose if necessary, rather than infrequent administration of a higher dose. Only continue treatment if it is judged to be in the best interests of the patient.

**7.2 Dose Escalation of THU-Dec**

Inter-individual differences in cytidine analogue metabolism (e.g., differences in CDA expression between individuals) are anticipated to require the ability to increase dose if necessary in some individuals in order to better achieve the intended molecular pharmacodynamic effect of non-cytotoxic DNMT1-depletion. The following considerations guide the option of dose escalation:

**If there is stable disease or partial response by RECIST v1.1 at the week 8 or 16 staging CTs, and there are no treatment-related ≥grade 3 toxicities (Table 1), and blood count trends (trends in the absolute neutrophil, absolute lymphocyte and platelet counts) suggest that such treatment-related toxicities are not imminent, then the dose of THU and Dec can be increased by one capsule each.** THU-Dec dose increases should not occur more often than every 4 weeks and only to a maximum of 2 additional capsules of each drug from the starting dosage. **ALTERNATIVELY**, if the patient is receiving oral THU-Dec 1X/week because of previous frequency reduction, the frequency of administration can be increased to 2X/week at the same dose of oral THU-Dec.

**7.3 Dose Modification or dose delay of Nivolumab**

No Dose modification for nivolumab is suggested. Because of the potential for clinically meaningful nivolumab-related AEs requiring early recognition and prompt intervention,

management algorithms have been developed for suspected AEs of selected categories. See Appendix III

Dose delay criteria apply for all drug-related adverse events (regardless of whether or not the event is attributed to nivolumab). If AE is felt to be immune related and attributable to nivolumab, if the patient is on the study arm they can continue THU-Dec while nivolumab is held.

Dose delay criteria apply for all drug-related AEs. Nivolumab must be delayed until treatment can resume

**Nivolumab administration should be delayed for the following:**

Any Grade  $\geq 2$  non-skin, drug-related AE, with the following exceptions:

- Grade 2 drug-related fatigue or laboratory abnormalities do not require a treatment delay
- Any Grade 3 skin, drug-related AE
- Any Grade 3 drug-related laboratory abnormality, with the following exceptions for lymphopenia, leukopenia, AST, ALT, total bilirubin, or asymptomatic amylase or lipase:
  - Grade 3 lymphopenia or leukopenia does not require dose delay.
  - If a subject has a baseline AST, ALT, or total bilirubin that is within normal limits, delay dosing for drug-related Grade  $\geq 2$  toxicity.
  - If a subject has baseline AST, ALT, or total bilirubin within the Grade 1 toxicity range, delay dosing for drug-related Grade  $\geq 3$  toxicity.

Any AE, laboratory abnormality, or intercurrent illness which, in the judgment of the investigator, warrants delaying the dose of study medication.

**Subjects who require delay of nivolumab should be re-evaluated closely as clinically indicated and resume nivolumab dosing when re-treatment criteria are met.**

**Criteria to Resume Treatment**

Subjects may resume treatment with study drug when the drug-related AE(s) resolve to Grade  $\leq 1$  or baseline value, with the following exceptions:

- Subjects may resume treatment in the presence of Grade 2 fatigue
- Subjects who have not experienced a Grade 3 drug-related skin AE may resume treatment in the presence of Grade 2 skin toxicity
- Subjects with baseline Grade 1 AST/ALT or total bilirubin who require dose delays for reasons other than a 2-grade shift in AST/ALT or total bilirubin may resume treatment in the presence of Grade 2 AST/ALT OR total bilirubin
- Subjects with combined Grade 2 AST/ALT AND total bilirubin values meeting discontinuation parameters should have treatment permanently discontinued

- Drug-related pulmonary toxicity, diarrhea, or colitis, must have resolved to baseline before treatment is resumed. *Subjects with persistent Grade 1 pneumonitis after completion of a steroid taper over at least 1 month may be eligible for retreatment.*
- Drug-related endocrinopathies adequately controlled with only physiologic hormone replacement may resume treatment.

If the criteria to resume treatment are met, the subject should restart treatment at the next scheduled timepoint per protocol. However, if the treatment is delayed past the next scheduled timepoint per protocol, the next scheduled timepoint will be delayed until dosing resumes.

If treatment is delayed or interrupted for > 6 weeks, the subject must be permanently discontinued from study therapy, except as specified in discontinuation section.

## **8.0 ADVERSE EVENTS AND POTENTIAL RISKS**

### **8.1 Decitabine**

Dec is manufactured by ScinoPharm (Taiwan) and formulated by KP Pharmaceutical Technologies (Bloomington, IN, USA) as per Federal Good Manufacturing Practice guidelines. Dec is supplied as capsules containing 5 mg of Dec per capsule, in bottles containing 8 capsules per bottle, together with a drying agent. Bottles should be tightly closed and stored at 2-8°C in the refrigerator. The label on the bottles includes the following information: the (i) name of the drug; (ii) quantity of drug per capsule; (iii) date of packaging; (iv) recommended storage temperature; (v) lot number of bulk drug used to generate the capsules.

*Side-Effects of Dec:* Dec is an intravenously-administered therapeutic which is FDA-approved for the treatment of the blood cancer myelodysplastic syndrome (MDS) under the brand name Dacogen. As such, the toxicology, pharmacology and ADME profile of Dec has been reviewed by the FDA (NDA #21,790).

There is substantial information regarding the toxicity of Dec in humans from clinical trials in patients with MDS and AML, including relapsed or poor prognosis cases. Some of this information is summarized in the package insert for this FDA approved drug. In almost all studies, the patients received doses much higher than the Dec doses planned in this study. Leukopenia was a major toxicity and nausea, or vomiting were common non-hematologic toxicities. A better guide to anticipated side-effects in this clinical trial are observations from clinical studies of Dec repositioned for non-cytotoxic DNMT1-depletion for sickle cell disease (SCD),  $\beta$ -thalassemia intermedia and MDS. In these clinical trials there were no episodes of non-hematologic NCI/CTEP grade 2 or higher toxicity from Dec. In the SCD and  $\beta$ -thalassemia trials, consistent with a non-cytotoxic mechanism of action, the main side-effect was an increase in the platelet count (as opposed to the usual side-effect of thrombocytopenia seen with cytotoxic treatments). Cytotoxicity/DNA damage assays based on bone marrow morphological examination, bone marrow DNA content analysis, VDJ recombination assay, erythrocyte micronucleus assay and gamma-H2AX assay were

also negative. These assays did not reveal evidence of DNA damage or cytotoxicity. The increase in the platelet count was not associated with any clinical adverse events, and specifically, without evidence by correlative studies for an increase in thrombotic tendency.

## **8.2 Tetrahydrouridine**

THU is a uridine analogue competitive inhibitor of CDA with a multi-decade track-record of safety in several clinical trials. THU does not have therapeutic utility as a separate entity, instead, it has been used to increase the activity of co-administered cytidine analogues in these clinical trials. In almost all these clinical studies, the intended pharmacodynamic effect of the co-administered cytidine analogue (e.g., cytarabine) was cytotoxicity, and toxicities were from the co-administered cytidine analogue and not from THU. Therefore, this clinical protocol contrasts with these previous studies in that THU is being used to create a pharmacologic profile of Dec that avoids cytotoxicity while simultaneously increasing non-cytotoxic DNMT1-depletion.

Currently, THU is being used in three NIH-sponsored clinical trials: at 350-500 mg/m^2 administered daily for 3-5 consecutive days in combination with 5-fluoro-2'-deoxycytidine (e.g. NCT00077051), or daily for 7 or more days in combination with other oncotherapeutics (e.g. NCT00378807, NCT00521183).

**Table 2: Clinical trials with tetrahydrouridine (THU) (published data).**

THU dose	THU Route	Combination drug	Number of patients	Toxicity attributed to THU?
350 mg/m  Q12 hours x 4 days	IV	IV Ara-C 100-200 mg/m  Q12 hours x 4 days	32	None reported
350 mg/m  daily x 5 days	IV	IV 5-fluoro-2'-deoxycytidine 5-80 mg/m  daily x 5 days	11	None reported
2,100 – 2,800 mg/m  total dose	IV	IV Ara-C 1,200 - 1,600 mg/m  and carboplatin 900 mg/m  total dose	8	Myelosuppression, unacceptable hepatotoxicity, diarrhea. No attribution to direct THU effect (attributed to Ara-C co-administered with THU)
2 - 4 mg/kg (approx 75-150 mg/m  ) for 3	oral	Oral 5-azacytidine 0.2mg/kg for 3	2	None reported

consecutive days every week		consecutive days every week		
25 – 50 mg/kg (approx 900 – 1800 mg/m  ) daily x 5 days	IV	IV Ara-C 0.1 – 0.2 mg/kg (approx 4 – 8 mg/m  ) daily x 5 days		None reported. Toxicities were as expected from Ara-C alone
200 mg/m  x 1	IV, SQ and oral	none	5	None reported

Side-Effects of THU: The single dose toxicology of THU was evaluated in dogs and Rhesus monkeys at intravenous doses of up to 1000mg/kg: with the exception of local inflammation at the injection site, no notable toxic effects were attributed to the administration of THU. Administration of THU to humans by the IV, SQ (SQ), and oral (PO) routes, in combination with various cytidine analogues, in studies spanning over 30 years, suggest it has a benign toxicity profile, including with oral administration for more than 1 year (summarized in **Table 2**). In a study of THU alone administered by IV, SQ and PO routes at a single dose of 200 mg/m^2 to 5 patients with malignant melanoma, there was no mention of toxicities. Similarly, THU administered at a daily dose of approximately 900-1800 mg/m^2 for 5 consecutive days together with cytosine arabinoside did not produce toxicities other than those expected with cytosine arabinoside alone. A similar experience is described when THU was administered at 700 mg/m^2 daily for 4 consecutive days together with cytosine arabinoside. Currently, THU is being used in three NIH-sponsored clinical trials: at 350-500 mg/m^2 administered daily for 3-5 consecutive days in combination with 5-fluoro-2'-deoxycytidine (e.g. NCT00077051), or daily for 7 or more days in combination with other oncotherapeutics (e.g. NCT00378807, NCT00521183).

Side-Effects of THU and decitabine in combination: In the Phase 1 clinical trial of oral THU and decitabine in combination administered 2X/week on consecutive days for 8 weeks at the doses used in this clinical trial, the side-effects of the combination treatment were the side-effects expected with non-cytotoxic DNMT1-depletion by decitabine, that is, an increase in the platelet counts and total hemoglobin concurrent with a decrease in the absolute neutrophil counts.

Astex Pharmaceuticals has evaluated the combination of an orally ingested THU analog (a fluorinated THU) in combination with oral decitabine 15-40 mg per day for 5 consecutive days repeated every 28 days to treat patients with myeloid malignancies. The dose of decitabine evaluated in combination with the THU analog was thus ~2-3X higher than the doses of decitabine used in this clinical trial. There were no significant non-hematologic adverse events attributed to the combination, with the main risks being related to myelosuppression as seen with similar doses of decitabine alone.

Side-Effects of Nivolumab: See section 1.4.2 and Nivolumab Investigator Brochure for information on the Adverse events of nivolumab, the standard of care drug in this protocol.

## 8.2 Definitions

### 8.2.1 Adverse Event

An Adverse Event (AE) is defined as any new untoward medical occurrence or worsening of a preexisting medical condition in a clinical investigation subject administered an investigational (medicinal) product and that does not necessarily have a causal relationship with this treatment. An AE can therefore be any unfavorable and unintended sign (such as an abnormal laboratory finding), symptom, or disease temporally associated with the use of investigational product, whether or not considered related to the investigational product.

The causal relationship to study drug is determined by a physician and should be used to assess all adverse events (AE). The casual relationship can be one of the following:

**Related:** There is a reasonable causal relationship between study drug administration and the AE.

**Not related:** There is not a reasonable causal relationship between study drug administration and the AE.

The term "reasonable causal relationship" means there is evidence to suggest a causal relationship.

Adverse events can be spontaneously reported or elicited during open-ended questioning, examination, or evaluation of a subject. (In order to prevent reporting bias, subjects should not be questioned regarding the specific occurrence of one or more AEs.)

### NONSERIOUS ADVERSE EVENT

- Nonserious Adverse Events are to be provided to BMS in aggregate via interim or final study reports as specified in the agreement or, if a regulatory requirement [e.g. IND US trial] as part of an annual reporting requirement.
- Nonserious AE information should also be collected from the start of a placebo lead-in period or other observational period intended to establish a baseline status for the subjects.

A *nonserious adverse event* is an AE not classified as serious.

#### Nonserious Adverse Event Collection and Reporting

The collection of nonserious AE information should begin at initiation of study drug. All nonserious adverse events (not only those deemed to be treatment-related) should be collected continuously during the treatment period and for a minimum of 30 days following the last dose of study treatment, unless they start other treatments for the cancer within that time, transition to hospice or expire within 30 days after treatment. AE evaluation can be done by chart review and/or telephone encounter.

Nonserious AEs should be followed to resolution or stabilization, or reported as SAEs if they become serious. Follow-up is also required for nonserious AEs that cause interruption

or discontinuation of study drug and for those present at the end of study treatment as appropriate.

### **Laboratory Test Abnormalities**

All laboratory test results captured as part of the study should be recorded following institutional procedures. Test results that constitute SAEs should be documented and reported as such.

The following laboratory abnormalities should be documented and reported appropriately:

- any laboratory test result that is clinically significant or meets the definition of an SAE
- any laboratory abnormality that required the subject to have study drug discontinued or interrupted
- any laboratory abnormality that required the subject to receive specific corrective therapy.

### **8.2.2 Serious Adverse Events**

#### **SERIOUS ADVERSE EVENTS**

A *Serious Adverse Event (SAE)* is any untoward medical occurrence that at any dose:

- results in death
- is life-threatening (defined as an event in which the subject was at risk of death at the time of the event; it does not refer to an event which hypothetically might have caused death if it were more severe)
- requires inpatient hospitalization or causes prolongation of existing hospitalization (see **NOTE** below)
- results in persistent or significant disability/incapacity
- is a congenital anomaly/birth defect
- is an important medical event (defined as a medical event(s) that may not be immediately life-threatening or result in death or hospitalization but, based upon appropriate medical and scientific judgment, may jeopardize the subject or may require intervention [eg, medical, surgical] to prevent one of the other serious outcomes listed in the definition above.) Examples of such events include, but are not limited to, intensive treatment in an emergency room or at home for allergic bronchospasm; blood dyscrasias or convulsions that do not result in hospitalization.)
- Potential drug induced liver injury (DILI) is also considered an important medical event.

- Suspected transmission of an infectious agent (eg, pathogenic or nonpathogenic) via the study drug is an SAE.
- Although pregnancy, overdose, and cancer are not always serious by regulatory definition, these events must be handled as SAEs.

The following hospitalizations are not considered SAEs in BMS clinical studies:

- a visit to the emergency room or other hospital department < 24 hours, that does not result in admission (unless considered an important medical or life-threatening event)
- elective surgery, planned prior to signing consent
- admissions as per protocol for a planned medical/surgical procedure
- routine health assessment requiring admission for baseline/trending of health status (eg, routine colonoscopy)
- Medical/surgical admission other than to remedy ill health and planned prior to entry into the study. Appropriate documentation is required in these cases
- Admission encountered for another life circumstance that carries no bearing on health status and requires no medical/surgical intervention (eg, lack of housing, economic inadequacy, caregiver respite, family circumstances, administrative reason).

### Potential Drug Induced Liver Injury (DILI)

Wherever possible, timely confirmation of initial liver-related laboratory abnormalities should occur prior to the reporting of a potential DILI event. All occurrences of potential DILIs, meeting the defined criteria, must be reported as SAEs. Potential drug induced liver injury is defined as:

- 1) ALT or AST elevation > 3 times upper limit of normal (ULN)  
AND
- 2) Total bilirubin > 2 times ULN, without initial findings of cholestasis (elevated serum alkaline phosphatase)  
AND
- 3) No other immediately apparent possible causes of AST/ALT elevation and hyperbilirubinemia, including, but not limited to, viral hepatitis, pre-existing chronic or acute liver disease, or the administration of other drug(s) known to be hepatotoxic.

### **Pregnancy**

If, following initiation of the investigational product, it is subsequently discovered that a study subject is pregnant or may have been pregnant at the time of investigational product

exposure, including during at least 6 half-lives after product administration, the investigational product will be permanently discontinued in an appropriate manner (eg, dose tapering if necessary for subject safety).

The investigator must immediately notify Worldwide Safety at BMS of this event via the Pregnancy Surveillance Form in accordance with SAE reporting procedures.

Follow-up information regarding the course of the pregnancy, including perinatal and neonatal outcome and, where applicable, offspring information must be reported on the Pregnancy Surveillance Form which is provided upon request from BMS.

Any pregnancy that occurs in a female partner of a male study participant should be reported to BMS. Information on this pregnancy will be collected on the Pregnancy Surveillance Form.

### **Overdose**

An overdose is defined as the accidental or intentional administration of any dose of a product that is considered both excessive and medically important. All occurrences of overdose must be reported as an SAE.

### **Other Safety Considerations**

Any significant worsening noted during interim or final physical examinations, electrocardiograms, x-rays, and any other potential safety assessments, whether or not these procedures are required by the protocol, should also be recorded as a nonserious or serious AE, as appropriate, and reported accordingly.

### **8.2.3 Adverse Event Evaluation**

The investigator or designee is responsible for ensuring that all adverse events (both serious and non-serious) observed by the clinical team or reported by the subject which occur after the subject has signed the informed consent are fully recorded in the subject's medical records. Source documentation must be available to support all adverse events.

A laboratory test abnormality considered clinically relevant (e.g., causing the subject to withdraw from the study, requiring treatment or causing apparent clinical manifestations, result in a delay or dose modification of study treatment, or judged relevant by the investigator), should be reported as an adverse event.

The investigator or sub-investigator (treating physician if applicable) will provide the following for all adverse events (both serious and non-serious):

- Event term (as per CTCAE)
- Description of the event
- Date of onset and resolution
- Expectedness of the toxicity
- Grade of toxicity
- Attribution of relatedness to the investigational agent- (this must be assigned by an investigator, sub-investigator, or treating physician)
- Action taken as a result of the event, including but not limited to; no changes,

dose interrupted, reduced, discontinued, etc. or action taken with regard to the event, i.e. no action, received conmed or other intervention, etc.

- Outcome of event

Descriptions and grading scales found in the NCI Common Terminology Criteria for Adverse Events (CTCAE) version 4.03 will be utilized for AE reporting.

An expected adverse event is an event previously known or anticipated to result from participation in the research study or any underlying disease, disorder, or condition of the subject. The event is usually listed in the Investigator Brochure, consent form or research protocol.

An unexpected adverse event is an adverse event not previously known or anticipated to result from the research study or any underlying disease, disorder, or condition of the subject.

Attribution is the relationship between an adverse event or serious adverse event and the study drug. Attribution will be assigned as follows:

- Definite – The AE is clearly related to the study drug.
- Probable – The AE is likely related to the study drug.
- Possible – The AE may be related to the study drug.
- Unlikely – The AE is doubtfully related to the study drug.
- Unrelated – The AE is clearly NOT related to the study drug.

Protocol must specify if attribution is required for individual components of the treatment regimen or the treatment regimen as a whole.

### **8.3 SAE Report Form**

SAEs will be recorded on the FDA Form 3500A (MedWatch) but should only be reported as instructed below. The electronic FDA SAE reporting forms should not be used.

### **8.4 Reporting Procedures for Serious Adverse Events**

Since there is an early stopping rule for this clinical trial (Section 6.4), all AEs related to toxicity that cause patients to withdraw from the study in the first 5 patients should be reported to the DSTC in “real-time”.

For the purposes of safety reporting, all adverse events will be reported that occur on or after Cycle 1 Day 1, through 30 days after the final dose of study drug. Adverse events, both serious and non-serious, and deaths that occur during this period will be recorded in the source documents. All SAEs should be monitored until they are resolved or are clearly determined to be due to a subject’s stable or chronic condition or intercurrent illness(es). Related AEs will be followed until resolution to baseline or grade 1 or stabilization.

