**- Frequency of THU and Dec ingestion:**

- THU ~10 mg/kg is administered 60 minutes before oral decitabine ~0.2 mg/kg 2X/week on consecutive days if there is no  $\geq$  grade 3 treatment-related non-hematologic toxicity and the ANC is  $>0.5 \times 10^9/L$  (if ANC is  $<0.5 \times 10^9/L$ , treatment is held until recovery above this threshold then resumed with a dose reduction as per Table 1).

- G-CSF neutropenia prophylaxis is recommended 1X/week if the ANC is  $<1.5 \times 10^9/L$

**Clinical Monitoring:** History and examination, laboratory tests, and regular radiologic assessments. Patients will continue study treatment until disease progression by clinical and/or radiologic parameters (RECIST v1.1), or unacceptable toxicity. Efficacy will be determined by radiographic evaluation and other measures as described above. THU-Dec safety profile will be determined by incidence of treatment emergent adverse events captured from the first dose of THU. Each adverse event will be summarized by grade, causality, expected/unexpected based on the current knowledge. Further, adverse events will be summarized by body system and at the patient level (worst grade for specified adverse event).

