#### **8.4.1 SAE Reporting Requirements**

Participating investigators (all sites) must report all serious adverse events to the Sponsor within **24 hours** of discovery or notification of the event. The participating investigator must also provide follow-up information on the SAE until final resolution. Sponsor contact:

- [name], [[contact]](mailto:[contact]) and research coordinator, [name], [[contact]](mailto:[contact])

The Sponsor will review the SAE and report the event to the FDA, external collaborator(s), and IRB as applicable.

It is the Sponsor-Investigator's responsibility (e.g. lead site PI) to ensure that ALL serious adverse events that occur on the study (e.g. ALL SAEs that occur at each enrolling institution) are reported to all participating sites.

All SAEs should simultaneously be faxed or e-mailed to BMS at:

Global Pharmacovigilance & Epidemiology  
Bristol-Myers Squibb Company  
[contact]  
Email: [[contact]](mailto:[contact])

- An SAE report should be completed for any event where doubt exists regarding its seriousness.
- For studies with long-term follow-up periods in which safety data are being reported, include the timing of SAE collection in the protocol.
- If the investigator believes that an SAE is not related to study drug, but is potentially related to the conditions of the study (such as withdrawal of previous therapy or a complication of a study procedure), the relationship should be specified in the narrative section of the SAE Report Form.
- If only limited information is initially available, follow-up reports are required. (Note: Follow-up SAE reports should include the same investigator term(s) initially reported.)
- If an ongoing SAE changes in its intensity or relationship to study drug or if new information becomes available, a follow-up SAE report should be sent within 24 hours to BMS using the same procedure used for transmitting the initial SAE report. All SAEs should be followed to resolution or stabilization. All SAEs should be followed to resolution or stabilization.

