- a) Patients will receive Nivolumab every 2 weeks ( $\pm$  4 days per protocol) (4 weeks i.e 2 treatments=1 cycle) until progression (by RECIST v1.1) or unacceptable toxicity. A treatment break for upto 6 weeks for will be allowed upon discussion with study PI
- b) Patients will be monitored post study every 12 weeks ( $\pm$  3 weeks) for post-study treatment status, clinical safety updates and survival; these could be done by review of patient's medical records or contacting patient's medical provider or the subject.
- c) Patients disease will be monitored with CT scans of the chest, abdomen and pelvis after every 2 cycles (i.e prior to every odd cycle  $\pm$  7 days) or sooner if clinically indicated;
- d) Patients who have recent ( $<$ 6 weeks from start of study treatment) tissue biopsy or patients who have had recurrence after surgery within 6 months of surgical resection may be eligible without a fresh biopsy; Rest of the patients will require a biopsy prior to study enrollment. Patients will require a repeat biopsy in 6-10 weeks post treatment prior to cycle 3 of nivolumab. If the biopsy is felt to be high risk by the treating physician or interventional radiologist, an exception may be made upon discussing with the PI.
- e) For Cycle 1 Day 1 (C1D1) labs, screening labs can be used if  $\leq$ 1 week; pregnancy tests need to be done within 24hrs of first dose.

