## 11.0 CORRELATIVE STUDIES

### ***Tumor Biopsies:***

***Percutaneous US or CT-guided core-needle biopsy:*** Patients are ineligible if they refuse percutaneous biopsy or if in the judgement of interventional radiology or pulmonologist the risk of significant complications exceeds 2%. If percutaneous biopsy is feasible, it is planned at protocol screening, between week 6-10, and at disease progression (biopsy at progression is mandatory if a subject wishes to cross-over). Where possible, FFPE tissue from the time of original diagnosis should also be obtained.

Percutaneous, bronchoscopy or surgical biopsies could be considered; The objective is to obtain 0.5-1.5 cm cores. The tissue samples are processed according to specifications in the correlatives/lab manual;

***Peripheral blood collections for PK and correlative studies:*** Patients will have baseline and follow up on treatment pre-treatment blood sample for correlatives to evaluate markers described in **section 1.6**; Detailed blood collection procedures, processing, handling and shipping information are provided in the accompanying **Laboratory Manual**.

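### The protocol contradicts itself on when adverse-event reporting starts; read literally, section 8.4 leaves serious complications of the required screening biopsy outside the reporting window

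*Combined protocol and SAP*

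**What the plan says.** Section 8.4 sets the window: "all adverse events will be reported that occur on or after Cycle 1 Day 1", and the window closes 30 days after the last dose. Its next sentence ties recording in source documents to the same period, and section 8.3 says that SAEs are to be reported only as the text after it instructs. For nonserious events, section 8.2.1 opens at essentially the same point: "The collection of nonserious AE information should begin at initiation of study drug".

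Other parts start earlier or give no start:

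- Section 8.2.3 makes the investigator responsible for seeing that events, serious or not, "which occur after the subject has signed the informed consent are fully recorded" in the medical records, and asks for term, grade, attribution, action and outcome.
- The study calendar (section 10.0) appears to mark adverse-event review at main screening, and section 12.2(c) has adverse-event assessments at baseline.
- Section 8.4.1 says that participating investigators "must report all serious adverse events to the Sponsor within" 24 hours, and explains how the narrative should describe an SAE that stems from the conduct of the study, such as a procedural complication.
- Section 8.6 makes each site's principal investigator responsible for getting all SAEs on the trial to the safety committee.

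On the biopsy, inclusion criterion 4 in section 4.1 requires agreement to a pre-study biopsy, with a waiver for suitable archival tissue or excessive risk. Calendar footnote d lists exemptions and then states: "Rest of the patients will require a biopsy prior to study enrollment". Section 11.0 makes a patient ineligible if, in the specialist's judgement, "the risk of significant complications exceeds 2" per cent. Section 12.2 evaluates safety only in randomized subjects who received at least one dose. The synopsis bases the THU-Dec safety profile on treatment-emergent events "captured from the first dose of THU".

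**The concern.** The biopsy is the most hazardous thing that the protocol asks of a patient before treatment. Section 13.2.1 requires consent before any study procedure, so the patient is already a participant when the needle goes in. If a pneumothorax or bleed at that point puts the patient in hospital, section 8.4 does not ask for a report, while section 8.2.3 asks for a full record and section 8.4.1 seems to want it within 24 hours. Two sites could each follow the protocol and treat the same event differently.

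What is at stake is oversight. Harm from a study procedure might not reach the sponsor or the safety committee, and the published account of the risk of taking part could be too favourable. The risk of missing the event is greatest for a patient who is harmed and then never dosed, because that patient appears in no safety table.

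**Working it through.** **Order of events.** The calendar puts main screening at Day -28 to Day -1, and footnote d puts the biopsy before enrollment. Every screening biopsy therefore precedes Cycle 1 Day 1. The week 6-10 biopsy falls inside the window for patients on treatment, so the gap concerns the screening biopsy.

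**Does each provision cover a serious screening-biopsy complication?**

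| Provision | Start | Covers it? |
|---|---|---|
| 8.2.1, definition of an adverse event | subject has been given an investigational product | not clearly, if undosed |
| 8.2.2, definition of an SAE | occurrence at any dose | not clearly, if undosed |
| 8.2.1, nonserious collection | study drug | no |
| 8.2.3, evaluation | consent | recorded and graded; no reporting route given |
| 8.4, reporting | Cycle 1 Day 1 | no |
| 8.4.1, SAEs to sponsor | none stated | yes if read alone; unclear as a subsection of 8.4 |
| 8.6, SAEs to safety committee | none stated | yes if read alone |
| 12.2, safety set | at least one dose | no, if never dosed |

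The one rule that dates SAE reporting excludes the event, and the rules that would include it carry no date. The text does not settle which governs.

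**The plan's own safety figure.** Section 3.2 uses P(at least one) = 1 - (1 - p)^n at p = 5%:

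- n = 20: 1 - 0.95^20 = 0.6415 (stated 64%)
- n = 40: 1 - 0.95^40 = 0.8715 (stated 87%)

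Both reproduce.

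**Scale of the gap, same formula.** Inputs: n = 60, the planned sample size (section 3.2), if every patient is biopsied; n = 30, assuming half are waived; p = 2%, the ceiling in section 11.0; p = 1% and 0.5%, assumed. Complications are taken as independent.

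| Risk per biopsy | n = 60: expected number | n = 60: chance of at least one | n = 30: expected number | n = 30: chance of at least one |
|---|---|---|---|---|
| 2% | 60 x 0.02 = 1.2 | 1 - 0.98^60 = 0.702 | 0.6 | 1 - 0.98^30 = 0.455 |
| 1% | 0.6 | 1 - 0.99^60 = 0.453 | 0.3 | 1 - 0.99^30 = 0.260 |
| 0.5% | 0.3 | 1 - 0.995^60 = 0.260 | 0.15 | 1 - 0.995^30 = 0.140 |

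Biopsies in patients who then fail screening would add to these numbers, but the documents give no count.

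**The case against.** The strongest reply is that the exclusion is not settled. Section 8.4.1 wants all SAEs within 24 hours and foresees complications of study procedures. Section 8.6 wants all of them to reach the safety committee, section 8.5 puts all of them in the trial database, and section 8.2.3 starts at consent. This stands. A reader might infer from section 8.4 that no screening-biopsy event is reportable and that the sponsor, safety committee and IRB would never see one. The documents do not support that: the provisions without a start date could be read to require a report, and section 8.4.1 is followed by an instruction that leaves IRB reporting to local IRB policy. What remains is that 8.4.1 sits under the 8.4 window and 8.2.3 is a duty to record, so neither clearly closes the gap.

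A reader might also count four different start points, adding the first dose of THU in the synopsis, and conclude that the windows differ by arm. In practice there are two, consent and first dose. Study-drug initiation and Cycle 1 Day 1 are in effect the same day. The synopsis phrase concerns only the THU-Dec safety profile, and section 6.2 refers to a Cycle 1 Day 1 dose of THU-Dec. A difference between the arms is not shown.

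It can further be said that a pre-dose event does not clearly meet the definitions in 8.2.1 and 8.2.2. That is correct, but it widens the gap and means that the definitions need attention too. Finally, a safety set of treated subjects is a reasonable choice for describing drug toxicity. That also stands: the treatment-emergent tables need not change, only be supplemented.

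**Conclusion.** The protocol is inconsistent on when adverse-event and SAE reporting starts, and its only dated SAE rule, followed literally, omits serious harm from a required screening procedure. The sponsor and safety committee may miss such an event; whether they would depends on which section a site follows. The inconsistency should be corrected.

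The illustrative chance of at least one significant complication before Day 1 runs from 14% (30 biopsies, 0.5% risk) to 70% (60 biopsies, 2% risk). The 70% should not be read as a forecast: 2% is the individual risk above which a patient is ineligible, not an expected rate; biopsies can be waived; and the protocol does not define a significant complication as an SAE. The 1% and 0.5% risks and the half-waived case are assumptions. The contradiction itself rests on the text alone and needs none of these figures. The primary endpoint, sample size and power are unaffected.

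**What to change.** Reconcile the adverse-event definition and nonserious-event text in 8.2.1, the SAE definition in 8.2.2, and sections 8.2.3, 8.4 and 8.4.1 around one rule:

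- Report SAEs, and any adverse event related to a protocol-required procedure, from informed consent to the existing end of the window (30 days after the final dose). State that this includes subjects not yet dosed, and word the definitions so that they do not exclude those subjects.
- Keep first dose of any study drug as the start of the treatment-emergent tables in both arms, and align the synopsis wording with it.
- Add a separate listing of biopsy-related events for all consented, biopsied subjects, including those never treated.

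The cost is protocol wording, a few extra SAE reports and one extra listing. The calendar already appears to provide for adverse-event review at screening, so no new visit is needed.
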